Recruitment was defined as the percentage of potentially eligible participants who approached the team and those who were, in fact, enrolled in the study. Recruitment characteristics were described to better map potential barriers, difficulties, and interest of participants in being part of the study. Previous remote cognitive training to older adults frequently shows high adherence and retention rates, such as 80% to > 94%; therefore, for the present study, we conceptualized intervention adherence as at least 80% of session completion (10/12 sessions within 6 weeks). Retention rate was conceptualized as the proportion of enrolled participants who completed 100% of the study, including all intervention sessions and the post-intervention assessment.

Primary Outcomes: Training Gains in the Breakfast Game and Near-Transfer

Similar to our previous studies, three game outcomes were generated after each game trial: (1) *Number of Correct Tables*, or the number of full tables completed under the correct rule (by tableware or by guest), with higher scores reflecting better performance; (2) *Cooking Time Discrepancy* (in seconds), reflecting the accuracy of cooking each food (i.e., the difference between the required and actual cooking times, averaged across all foods); and (3) *Cooking Stop Time Difference* (in seconds), reflecting the synchrony of finishing the foods together (i.e., the difference between the first and last food stopped). For both measures, lower scores indicated better performance.

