The Alphanumeric Task under the 80% priority condition was one of the primary near transfer outcomes. In this condition, the participants were asked to prioritize one task over the other (e.g., Alphanumeric Equation or the Visual Detection task); therefore, this condition was the closest related to the EmCh approach, and more likely to serve as a transfer measure. The two variables under the 80% priority condition were: 1) *Alphanumeric Task 80% on Detection Task - Total Correct*, and 2) *Alphanumeric Task 80% on Equation Task – Total Correct*. Furthermore, based on a previous model of executive control, we created an Executive Control Composite Score based on measures of working memory (Letter-Number Sequencing total score), cognitive flexibility (WSCT – perseverative responses), inhibitory control (Stroop Color-Word Test-DKEFS Condition 3 – Inhibition, and Condition 4 - Inhibition and Switching), and divided attention (UFOV – Divided Attention Accuracy)⁶⁶. The composite score was created by summing the z-scores of each of the five tests.

Secondary Outcomes: Distant Transfer Outcome

Additional measures were used to assess potential psychosocial changes after the intervention, including the measure of self-efficacy (GSE), engagement in cognitive activities (CLAS), and mood questionnaires targeting symptoms of depression (BDI) and anxiety (BAI).

Acceptability: Post-Intervention Questionnaire

Acceptability was assessed based on participants' quantitative and qualitative responses in the post-intervention questionnaire⁵. Participants were asked to provide scores (0 to 10) and their views on specific aspects of the cognitive training program. For instance, they were asked to provide scores on the difficulty and enjoyability of the game, clarity of instructions, and accessibility of the platform. They were also asked to rate their overall experience in the study. Moreover, participants were asked to answer open-ended questions about the game and its influence on their daily lives.

Statistical Analysis

For the sample size calculation, we considered our previous preliminary data and the flat rule of thumb of at least 30 subjects to estimate a parameter. Therefore, the current sample size ($N=38$) would overcome the sample size from previous similar studies, including 10 young adults, and 15 to 18 older adults per group. The power analysis was conducted with the assumption of 5% attrition between evaluations, having 80% power at $\alpha=0.05$.

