At baseline, the overall sample was described, and comparisons between groups were assessed. The Independent samples T-test was applied for the continuous variables, and chi-squared tests were used for the categorical variables. All outcomes were analyzed following the intent-to-treat principle. To evaluate intervention effects, linear mixed models (LMM) were conducted using the lme4 R package (version 4.5.0). Each model included fixed effects for time (pre vs. post; or session 1 vs. session 12 on the Breakfast Game outcomes), group (experimental vs. control), and the interaction between time and group, with a random intercept for each participant to account for within-subject correlation. Baseline cognitive performance was included as a covariate in all LMM to control for individual variability at baseline. The primary analysis tested time-by-group interactions in the training gains and near-transfer measures, and the secondary analysis examined interactions in the distant transfer measures. Of note, all the Breakfast Game outcomes were based on the trial performance across sessions.

Multiple-comparison corrections across all six outcomes were performed to control the false discovery rate (FDR) using the Benjamini-Hochberg (BH) procedure. Adjusted p-values (q-values) less than 0.05 were considered significant. In addition, effect sizes (Cohen's d) were calculated for the outcome that presented a significant time-by-intervention group interaction. All analyses and visualizations were performed using the R Studio software (version 4.3.1).

Supplementary Material

Figure 1S. CONSORT Check List

CONSORT 2010 checklist of information to include when reporting a randomised trial*			
Section/Topic	Item No	Checklist item	Reported on page No
Title and abstract	1a	Identification as a randomised trial in the title	1
	1b	Structured summary of trial design, methods, results, and conclusions (for specific guidance see CONSORT for abstracts)	2
Introduction			
Background and objectives	2a	Scientific background and explanation of rationale	3-5
	2b	Specific objectives or hypotheses	5
Methods			
Trial design	3a	Description of trial design (such as parallel, factorial) including allocation ratio	5-6
	3b	Important changes to methods after trial commencement (such as eligibility criteria), with reasons	NA
Participants	4a	Eligibility criteria for participants	6-7
	4b	Settings and locations where the data were collected	6-7

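### The 80% power claim for N=38 names no effect size and is set at an unadjusted 0.05, which is not the six-outcome Benjamini-Hochberg rule by which the trial declares significance

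*Combined protocol and SAP*

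**What the plan says.** All of the relevant text is in the Statistical Analysis section of the combined protocol and SAP.

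- **Basis for N.** The authors write that "we considered our previous preliminary data and the flat rule of thumb of at least 30 subjects to estimate a parameter". They add: "Therefore, the current sample size ($N=38$) would overcome the sample size from previous similar studies". For older adults, they put the size of those earlier studies at 15 to 18 in each group.
- **Power.** "The power analysis was conducted with the assumption of 5% attrition between evaluations, having 80% power at" an alpha of 0.05. No outcome, effect size, SD, pre-post correlation, test or sidedness is attached to this figure. Cohen's d appears only later, as a quantity to be calculated once an interaction is significant.
- **Decision rule.** "Multiple-comparison corrections across all six outcomes were performed to control the false discovery rate (FDR) using the Benjamini-Hochberg (BH) procedure". A q-value below 0.05 counts as significant. The plan does not list the six outcomes at that point, but the outcome sections give six primary measures: three game scores, two Alphanumeric Task scores and the Executive Control Composite.
- **Model.** The test is the time-by-group interaction in a linear mixed model with a participant intercept and baseline performance as a covariate.

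**The concern.** Power is defined only for a stated effect, so a bare 80% cannot be checked or interpreted. The alpha in the power sentence is also not the criterion that an outcome must meet. A single comparison at 0.05 is easier to pass than BH over six, and the power sentence makes no allowance for the difference.

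What is at stake is how null results are read. The Objectives section hypothesises greater training gains and transfer effects in the experimental group, and the plan judges this by significance. A reader told that the trial had 80% power could take a non-significant transfer result as informative, although moderate effects had little chance of being declared significant.

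**Working it through.** **Can the plan's figure be reproduced?** No. Without an effect size, 80% at 0.05 can only be solved backwards for the effect it implies.

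**Inputs from the plan.** N=38, 1:1 allocation, 5% attrition, alpha 0.05, 80% power, BH over six outcomes at q<0.05.

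**Assumptions.** 38 is the total: 38/2 = 19 per arm is just above the earlier 15 to 18 per group. Tests are two-sided.

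**Step 1: evaluable sample.** 38 × 0.95 = 36.1, so about 18 per arm.

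**Step 2: effect implied at unadjusted 0.05.** With two time points, the time-by-group interaction is a between-arm comparison of change. The calculation uses a two-sample t-test with noncentrality d × √(n/2) and 2n − 2 degrees of freedom, where d is in SDs of the analysed quantity (change score or baseline-adjusted residual).

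| Per arm | d for 80% at 0.05 | d for 80% at 0.05/6 = 0.0083 |
|---|---|---|
| 19 (no attrition) | 0.93 | 1.19 |
| 18 (5% attrition) | 0.96 | 1.22 |
| 15 (20% loss: 38 × 0.80 = 30.4) | 1.06 | 1.36 |

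The value 0.05/6 is the first BH step, the strictest threshold an outcome can face. One-sided at 0.05, the detectable d would be 0.82 (19 per arm) to 0.85 (18 per arm). If 38 were per arm, it would be 0.65 to 0.67 two-sided.

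**Step 3: power under BH.** BH rejects the k smallest p-values, where k is the largest rank with p(k) ≤ 0.05 × k/6. The loosest threshold, at k=6, is 0.05 itself, so per-outcome power under BH can never exceed power at unadjusted 0.05. Simulation with six outcomes, 18 per arm and d=0.96 (80% at 0.05) gives the figures below. The between-outcome correlation was 0 to 0.6 for the power column, and 0 and 0.3 for the last column.

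| Outcomes with a true effect | Per-outcome power under BH | Loss from 80% | d needed for 80% under BH |
|---|---|---|---|
| 1 | about 54% | about 26 points | about 1.22 |
| 3 | 65-67% | 13-15 points | about 1.09 |
| 6 | 74-77% | 3-6 points | about 1.00 |

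**Step 4: a moderate effect.** For d=0.5 in the same SD, with 18 per arm, power is 31% at unadjusted 0.05. Under BH it is about 12% with one true effect, rising to about 20% with six true effects and outcome correlation 0.6.

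**Step 5: conversion to raw outcome SDs.** The models adjust for baseline, so the residual SD is the raw SD × √(1 − r²), where r is the pre-post correlation. The plan gives no r, so these values are assumed.

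| Assumed r | √(1 − r²) | At 0.05 (0.96 × factor) | At first BH step (1.22 × factor) |
|---|---|---|---|
| 0.5 | 0.866 | 0.83 | 1.06 |
| 0.7 | 0.714 | 0.69 | 0.87 |
| 0.8 | 0.600 | 0.58 | 0.73 |

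For an unadjusted change score the factor is √(2(1 − r)). It gives 0.96, 0.74 and 0.61 at 0.05 for the same three values of r.

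**The case against.** **A larger unstated effect would rescue the 80%.** With a planning effect of 1.22 SD or more, power would reach 80% even at the first BH step. But power at unadjusted 0.05 would then be about 94%, not the stated 80%. If the sentence is taken as written, power under BH is lower.

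**The detectable effect depends on the SD.** This stands. A reader might infer that the trial could detect only differences near or above one raw SD. The documents do not support that: with baseline adjustment and r of 0.7 to 0.8, the figure at 0.05 is 0.69 to 0.58 raw SD.

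**The first BH step is the worst case.** This also stands. The hypothesis is of benefit on training and transfer alike, and if all six effects are real the loss is only 3-6 points. Quoting 0.05/6 alone would present BH as Bonferroni.

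**Attrition.** A reader might infer that 5% attrition contradicts the Recruitment, Adherence, and Retention section, which says that earlier remote training "frequently shows high adherence and retention rates, such as 80% to > 94" per cent. It does not. The upper end is open, so the implied loss runs from 20% to under 6%, and 5% lies within that. The cited range also covers adherence and retention together, and the plan's own retention definition (every session plus the post-intervention assessment) is stricter than loss between evaluations. A 20% loss is a sensitivity case only.

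**It is a pilot, and it is finished.** Feasibility is the first aim, and recruitment and interventions ended in July 2024. Nothing in the documents treats non-significance as absence of effect; that is a risk for the reader, not something the plan says. This lowers the severity but does not make the power sentence correct.

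**Conclusion.** The point holds. The 80% is tied to no effect and to an alpha that is not the decision rule. If it is exact at 0.05, per-outcome power under BH is about 54% to 77%, depending on how many of the six outcomes have true effects.

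The figures assume that 38 is the total, 18 per arm after attrition, two-sided tests, a common effect across the outcomes that have one, and between-outcome correlation of 0 to 0.6. The translation to raw SDs rests on pre-post correlations that the documents do not give.

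It does not follow that N should have been larger, that the attrition assumption is wrong, or that the analysis is invalid. The correction is worth making but not critical: it changes how the results are described, and no test or estimate.

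**What to change.** Leave N and the account of how it was chosen (preliminary data, rule of thumb, earlier group sizes) as they are. Replace the power sentence with text along these lines, labelled as computed from the achieved design:

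> With 38 randomised and 5% attrition (18 per arm, two-sided), power is 80% at unadjusted 0.05 for a between-arm difference of 0.96 SD of the change score or baseline-adjusted residual. Under BH over six outcomes, 80% per-outcome power needs about 1.22, 1.09 or 1.00 SD if one, three or all six outcomes have a true effect. A difference of 0.5 SD has about 31% power at 0.05 and 12-20% under BH. With baseline adjustment and assumed pre-post correlations of 0.5, 0.7 and 0.8, the detectable effects in raw outcome SDs are 0.83, 0.69 and 0.58 at 0.05, and 1.06, 0.87 and 0.73 at the first BH step. A non-significant result is not evidence of no effect.

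A 20% loss (15 per arm: 1.06 SD at 0.05, 1.36 SD at the first BH step) may be added as a sensitivity case. If a calculation with a planning effect does exist, its outcome, effect, SD, correlation and test should be reported beside these figures.

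The cost is text only. The downside is that the stated figure becomes less favourable.

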The structure of sessions was consistent across the 12 sessions and included: split screen mode, eight game rounds lasting 4.5 minutes each, resulting in a session of 45 minutes. Participants were instructed not to complete more than one session per day, which was also enforced by the platform, as it would not allow two sessions on the same day, and to avoid gaps of more than four days between sessions. The intervention protocol is summarized in the Supplementary Material (Figure 2S). Briefly, in session 1, participants from both groups played the game without receiving any EmCh instructions, serving as a baseline session. During sessions 2 through 11, the experimental group received EmCh instructions, which directed their attention both within the Cooking task only and across the Cooking and Table Setting tasks. In contrast, the control group continued to play the game without EmCh instructions in all sessions, following the standard gameplay format. Session 12 mirrored session 1 and functioned as a post-EmCh assessment, with both groups playing the game without EmCh instructions. Furthermore, as illustrated in Figure 1 (highlighted in red and yellow circles), during sessions 1, 10, 11 and 12,

all participants played the 8 rounds of the game in a “full game” format (Table + Cooking); while in sessions 2 to 9, the game was played in a “partial” format, with 4 rounds of the game as “cooking only” and 4 rounds as “full game”. We implemented this approach to facilitate EmCh use in different game formats. To ensure clarity and support adherence to the protocol, the research team monitored participant performance through the platform system and supervised sessions 1, 2, 5, and 12 (30% of the sessions) through videoconference.

Outcomes

Recruitment, Adherence, and Retention

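### The baseline covariate in the pre/post mixed models cannot adjust the time-by-group test, so the primary estimate is the raw difference in change

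*Combined protocol and SAP*

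**What the plan says.** The Statistical Analysis section of the combined protocol and SAP sets out one model for all intervention effects. "Each model included fixed effects for time (pre vs. post; or session 1 vs. session 12 on the Breakfast Game outcomes), group (experimental vs. control"), together with their interaction, "with a random intercept for each participant to account for within-subject correlation". On the covariate it says: "Baseline cognitive performance was included as a covariate in all LMM to control for individual variability at baseline". On the test: "The primary analysis tested time-by-group interactions in the training gains and near-transfer measures". The secondary analysis looks at the same interaction for the distant-transfer measures. No covariate-by-time term is listed, and the covariate is not defined further.

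Two other statements decide how far the point reaches. Under the distant-transfer outcomes, "Additional measures were used to assess potential psychosocial changes after the intervention"; these are the GSE, CLAS, BDI and BAI, and they fall under the same model. For the game, the plan says that "all the Breakfast Game outcomes were based on the trial performance across sessions", and each session consists of "eight game rounds lasting 4.5 minutes each". It does not say whether a row in the game models is a single round or a session average.

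**The concern.** The plan gives the covariate a clear job: to take account of differences between participants at baseline. The quantity tested is the difference between groups in change from pre to post, which is formed within participants. A value that is the same on a participant's pre and post rows drops out of that contrast. Readers would take the primary results as baseline-adjusted when they are not.

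In a trial of this size, chance baseline imbalance is a practical issue, and the precision that adjustment offers is worth having. There is also a possible side effect. If the covariate is the outcome's own baseline, the same number appears on both sides of the equation for every pre row, which can distort the variance estimate. The model serves six primary outcomes (three game scores, two Alphanumeric scores, one composite) and four distant-transfer outcomes.

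**Working it through.** **Inputs.** The model terms are those quoted. N=38 and 5% attrition come from the Statistical Analysis section. N=38 is not labelled as total or per arm; I take it as the total, so 19 per arm. The pre/post correlation rho is not given; I use 0.3 to 0.8. Outcome SD is set to 1. The plan states no standard error or type I error for these models, so there is no figure to reproduce. N=38 itself cannot be re-derived, because no effect size is given.

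**Step 1: the estimate.** For participant i with group G, covariate c and time t = 0, 1:

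Y(i,t) = a + b·t + g·G(i) + d·t·G(i) + k·c(i) + u(i) + e(i,t)

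Subtracting the pre row from the post row:

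Y(i,1) − Y(i,0) = b + d·G(i) + e(i,1) − e(i,0)

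The terms k·c(i) and u(i) cancel. With complete pairs, the estimate of d is the difference in mean change, whatever c is. In simulated data, fitted with own baseline, with another covariate and with none, the largest gap between the two was 1.4e-15. The cancellation also holds for round-level rows if each participant has the same number of rounds in both sessions.

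**Step 2: what is lost.** Chance baseline imbalance has standard error sqrt(2/19) = 0.32 SD. The change contrast carries −(1−rho) times any imbalance: at rho 0.5, a one-standard-error imbalance moves it by 0.5 × 0.32 = 0.16 SD. For precision:

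| rho | Change SE, sqrt(4(1−rho)/19) | ANCOVA SE, sqrt(2(1−rho²)/19) | Variance ratio, (1+rho)/2 |
|---|---|---|---|
| 0.3 | 0.384 | 0.309 | 0.65 |
| 0.5 | 0.324 | 0.281 | 0.75 |
| 0.7 | 0.251 | 0.232 | 0.85 |
| 0.8 | 0.205 | 0.195 | 0.90 |

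Simulated mean SEs agree: 0.380, 0.322, 0.249 and 0.204 for change (two rows, no covariate), and 0.312, 0.283, 0.233 and 0.197 for ANCOVA. At rho 0.5, a change analysis would need about 38/0.75 = 51 participants to match ANCOVA on 38.

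**Step 3: standard error if c is the outcome's own baseline, one row per time point.** Write post = rho·pre + e, with Var(e) = 1 − rho².

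- Within-person mean square: (2 − 2·rho)/2 = 1 − rho.
- Between-person mean square after regression on baseline: 2 × (1 − rho²)/4 = (1 − rho)(1 + rho)/2, which is always smaller.
- Implied intercept variance: half the difference, −(1 − rho)²/4. REML therefore tends to its zero boundary.
- Pooled residual variance: about (1 − rho)(3 + rho)/4, so reported SE / true SE is about sqrt((3 + rho)/4).

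Null simulation, 19 per arm, complete data, 4,000 trials per value:

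| rho | SE ratio, formula | SE ratio, simulated | Intercept variance zero | Type I, residual df | Type I, N−2 df |
|---|---|---|---|---|---|
| 0.3 | 0.908 | 0.911 | 99.9% | 7.3% | 7.0% |
| 0.5 | 0.935 | 0.933 | 98.9% | 7.4% | 6.9% |
| 0.7 | 0.962 | 0.968 | 92.0% | 6.1% | 5.7% |
| 0.8 | 0.975 | 0.987 | 83.9% | 5.5% | 5.3% |

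The Monte Carlo standard error near 5% is sqrt(0.05 × 0.95/4000) = 0.3 points. With 18 per arm and 40,000 trials per value, type I error with N−2 df was 7.3%, 6.5%, 5.8% and 5.7%.

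**Step 4: another cognitive measure as c.** The SE ratio is 0.98 to 1.00 and type I error 4.9% to 5.6%, which is no material error.

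**Step 5: round-level rows for the game.** With eight rows per session and only a random intercept, type I error ran from about 7% to 33% under the assumed variances. It was much the same with and without the covariate (32.2% with own baseline, 31.6% without, at rho 0.5). The cause there is the absence of a participant-by-session effect.

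**The case against.** The strongest reply is that the difference in change is unbiased under randomisation, and that the two-row model without the covariate holds its level (4.9% to 5.3% in these simulations). On that view the point is one of efficiency in a stage 1B pilot. This stands in part: the estimate is not biased over repeated randomisations. It is still unadjusted, contrary to what the plan says the covariate is for, and it carries whatever imbalance this one small trial happened to have.

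A reader might go further and infer that every model uses the outcome's own baseline twice, so that all p-values entering the FDR step are too small. The documents do not support that, for three reasons. The covariate is described only as baseline cognitive performance and is never tied to the outcome being modelled. Read literally, it cannot be the own baseline of the self-efficacy, leisure-activity or mood scales. And if game rows are single rounds, the two-row algebra does not apply to three of the six primary outcomes; any inflation there has another cause. Even on the own-baseline reading, the reported SE at rho 0.5 (0.302) is larger than the ANCOVA SE (0.283). It is too small only for the change estimate it accompanies.

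A last reply is timing. The Study Design section says that recruitment and interventions ended in July 2024, so a new primary estimator is post hoc. That is right, and it governs how the change must be labelled. It does not make the present model adjust for baseline.

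**Conclusion.** The point holds for the estimate under any reading of the covariate: with complete pairs, the time-by-group test is the raw difference in change, and the stated control for baseline is not achieved. Proper adjustment would cut the variance by 25% at rho 0.5 and 15% at rho 0.7.

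The standard-error effect is conditional and modest. It needs the own-baseline reading and one row per time point. The random-intercept variance is then zero in about 84% to 99.9% of simulated trials, and type I error is about 5.5% to 7.4% with residual df, or 5.3% to 7.0% with N−2 df, for rho 0.8 to 0.3. The plan does not state a df method. With a different cognitive covariate the effect is immaterial.

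These sizes assume 19 per arm, complete data and the stated range of rho. With incomplete pairs the cancellation is no longer exact; I have not quantified that case.

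**What to change.** Drop the baseline covariate from the two-row models and name the baseline used for each outcome. Then use one of the following:

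- ANCOVA of the post score on group and that outcome's own baseline. For the game outcomes, regress the session-12 participant mean on group and the session-1 participant mean.
- A constrained-baseline model: time and time-by-group, a common baseline mean with no group main effect, and an unstructured 2×2 within-person covariance. This also keeps participants who have a baseline score only, which suits the intent-to-treat statement.

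State whether game rows are rounds or session means. If rounds are kept, add a participant-by-session random effect; removing the covariate alone would not cure the inflation in step 5. Report the adjusted post-training group difference with its 95% CI, recompute the FDR step, and label the analysis as a change made after data collection.

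The cost is revised wording and a re-run of ten models (six primary, four distant-transfer) on data already collected. Some p-values may become less favourable, and the post hoc status must be disclosed.

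### The plan does not state the unit of analysis for the Breakfast Game outcomes; if rounds are rows, a random intercept alone makes the time-by-group test anti-conservative

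*Combined protocol and SAP*

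**What the plan says.** The section on primary outcomes describes how the game is scored: "three game outcomes were generated after each game trial" (correct tables, cooking time discrepancy and cooking stop time difference). The section on sessions 1 to 12 fixes the session structure as "split screen mode, eight game rounds lasting 4.5 minutes each". That section and Figure 2S show sessions 1 and 12 as full-game sessions of eight rounds in both groups.

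The Statistical Analysis section gives one model for every outcome. The fixed effects are time, group and time-by-group, plus a baseline covariate. The random part is specified "with a random intercept for each participant to account for within-subject correlation". For the game outcomes, time is session 1 versus session 12. The primary test is the time-by-group interaction. The section then adds: "Of note, all the Breakfast Game outcomes were based on the trial performance across sessions". It gives no averaging rule, number of rows, further random term or degrees-of-freedom method.

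**The concern.** The interaction compares gains between randomised groups. Its proper error term is the variation in gain from person to person, with about as many degrees of freedom as there are participants. A random intercept removes stable differences in level between people. It cannot represent differences in how much people improve.

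With one value per person per session this does no harm, because the residual of the intercept-only model then contains the variation in gain. With eight rows per person per session, most of the residual degrees of freedom come from round-to-round scatter within a session. Variation in gain is diluted in that pool, and extra rounds are credited as evidence about the group difference that they do not carry. Equal true gain for everyone in a group is hard to assume over 12 training sessions.

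At stake are the three training-gain tests, which carry the hypothesis of greater gains with Emphasis Change. The two Alphanumeric totals and the executive composite appear to have one value per time point and are not directly affected. They do appear to share the Benjamini-Hochberg family of six (three game outcomes, two Alphanumeric, one composite).

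**Working it through.** **The plan's own figures.** The plan states N = 38, 80% power, alpha 0.05 and 5% attrition, but no effect size or SD, so N = 38 cannot be reproduced. No error rate is given for the game models beyond the nominal 5%, and that is the figure checked here.

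**Inputs**
- From the documents: 1:1 allocation; 8 rounds in each of sessions 1 and 12; participant random intercept only; N = 38.
- Assumed: N = 38 is the total, so 19 per group. Allowing for 5% attrition, 38 × 0.95 ≈ 36, or 18 per group.
- Assumed: the round-to-round SD is 1, and g is the SD of true gains between people in that unit. The documents give no value for g, so a range starting at zero is used.

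**Step 1: true variance.** One person's difference between session means has variance g² + 2/8 = (1 + 4g²)/4. The true variance of the interaction contrast is therefore proportional to 1 + 4g².

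**Step 2: what the intercept-only model uses with trial rows.** There are 38 × 16 = 608 rows. The residual pools 14 × 38 = 532 degrees of freedom from rounds within sessions (mean square 1) with 38 − 2 = 36 from gains (mean square 1 + 4g²):

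s² = [532 + 36(1 + 4g²)]/568 = 1 + 0.2535g²

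**Step 3: consequences.** The SE is too small by the factor F = √[(1 + 4g²)/s²]. The type I error is about 2[1 − Φ(1.964/F)], where 1.964 is the two-sided 5% point of t on 568 degrees of freedom.

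Example with g = 0.5: the true variance is 2.00 and s² = 1.063. So F = √(2.00/1.063) = 1.37, and the type I error is 2[1 − Φ(1.43)] = 15.2%.

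| g | 1 + 4g² | s² | F | Type I error |
|---|---|---|---|---|
| 0 | 1.00 | 1.000 | 1.00 | 5.0% |
| 0.1 | 1.04 | 1.003 | 1.02 | 5.4% |
| 0.2 | 1.16 | 1.010 | 1.07 | 6.7% |
| 0.3 | 1.36 | 1.023 | 1.15 | 8.9% |
| 0.5 | 2.00 | 1.063 | 1.37 | 15.2% |
| 0.7 | 2.96 | 1.124 | 1.62 | 22.6% |
| 1.0 | 5.00 | 1.253 | 2.00 | 32.5% |

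Simulated null trials with 18 and with 19 per group agree: about 5%, 5%, 7%, 9%, 15%, 22-23% and 32-33%.

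**Step 4: same check on another scale.** Let r be the share of within-person variance that lies between sessions, r = (g²/2)/(g²/2 + 1). For r = 0, 0.02, 0.05, 0.10, 0.20 and 0.30, the type I error is 5.0%, 6.7%, 9.5%, 14.2%, 22.9% and 30.3%. The value g = 0.5 is r = 0.11, so the two scales agree.

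**Step 5: what does and does not remove it**
- Baseline covariate: it is constant over a person's rows and does not touch the within-person contrast. In simulation the rejection rate with it was 13.3% at r = 0.10 and 32.2% at r = 0.30.
- More participants: at N = 76 the rates are essentially unchanged.
- Session means (76 values instead of 608): simulated rejection was 4.5% to 5.9% without the covariate and 4.5% to 6.3% with it.

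**Step 6: multiplicity.** Benjamini-Hochberg compares the k-th smallest of six p-values with k × 0.05/6. If three game p-values already pass, the next outcome is judged at 4 × 0.05/6 = 0.033. Ranked first, it would be judged at 0.05/6 = 0.008.

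**The case against.** The strongest reply is that no sentence says rounds are rows. Scoring after each trial describes data collection, and outcomes based on trial performance could be session scores built from trials. The common template, with pre versus post for some outcomes and session 1 versus session 12 for others, also fits one value per occasion. This stands: a reader might infer that trial-level analysis is established, and it is not. Trial rows remain the more natural reading, because the plan makes a special note of trial performance and gives no averaging rule.

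Second, a reader might infer that the model treats rounds as wholly independent. It does not. The intercept absorbs stable correlation within a person; the gap is specific to the interaction.

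Third, inflation needs real variation in gain. With g of 0 or 0.1 there is practically none, and the documents cannot say where g lies. Nor do they support saying that game p-values would dominate the Benjamini-Hochberg ranking, since that depends on the other p-values and on the true effects. The most that can be said is that spuriously small ones could loosen the threshold for the rest.

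**Conclusion.** The point holds conditionally. The documents leave open whether the three game models use rounds or session means, and the validity of their primary test turns on that. With trial rows and only a participant intercept, the interaction's standard error is too small whenever true gains differ between people. The nominal 5% test then rejects from about 5% (no variation in gain) through about 15% (gain SD half the round-to-round SD) to 32-33% (gain SD equal to it). These figures assume 18 to 19 per group, complete and balanced rounds, normal errors, and a range of g that is not taken from the documents. With session means the test holds about 5%. It does not follow from the documents that the reported training-gain tests are wrong.

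**What to change.** State the unit of analysis for the game outcomes and make the model match it, in one of two ways:

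- Average the eight rounds to one value per participant per session for each outcome, and keep the random intercept.
- Keep trial rows and add a by-participant random session effect (a random slope for session) to the intercept.

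In either case, test the interaction on participant-level degrees of freedom (about 36 with 38 participants, not 568), and say how they are obtained. With balanced rounds the two options should give essentially the same test; the second was not simulated.

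If session means were already used, the cost is one sentence. If trial rows were used, the three game models must be re-run and the Benjamini-Hochberg adjustment recomputed over all six outcomes. The downside is that the training-gain p-values may become less favourable.
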